### Focus Groups

Participants will be invited to attend one focus group interview with 6-8 other participants, again using the UTN-supported videoconference platform, and within 8 weeks of completing the last group session (VCI or AC). The purpose of the focus group is to collect data directly from participants regarding satisfaction with the program, e.g. program content, videoconference platform, development of community, support, suggestions for improvement, etc. Participants receive \$20 for attending the focus group. A questionnaire with the same questions asked in the two randomized groups will be completed by participants via a secure, web-based data management system (REDCap) upon completion of the focus group or completed on a paper document kept in a secure locked cabinet in the College of Nursing until data can be entered into REDCap..

## **Statistical Methods, Data Analysis and Interpretation**

---

Enrollment and randomization will continue until the following enrollment goals are met: Urban Latinas = 60 (n = 30 VCI; 30 AC); Rural Latinas = 60 (n = 30 VCI; 30 AC); Urban, North European-descent (NED) = 60 (n = 30 VCI; 30 AC); Rural NED = 60 (n = 30 VCI; 30 AC), for a total of 240 participants.

### **Data Analysis:**

We will compare demographics, partum group, and medications between groups ( $\chi^2$ ) to document the results of our randomization process. We will further document and test for differences in frequency and means in groups related to additional study-related variables. Examples include dose of participation and birth complications or pre-term deliveries. We will explore the addition of these variables in our analytical models.

We will utilize multilevel generalized mixed modeling (via SPSS and R) under an intent-to-treat (ITT) approach to compare the outcome measures of EPDS and GAD-7 between Group 1 (VCI) and Group 2 (AC) at up to six time points. To assess whether we will need to nest participants within clusters (Level 3, group-level) given that the intervention/control are administered in groups, we will conduct an analysis that adds an additional level (nesting participants within clusters) to our proposed model and calculate the model's ICC. As an exploratory analysis, for both aims, we will add the fixed effect of baby's sex to final models and report results.

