
## Purpose and Objectives

---

The study will evaluate the effectiveness of a videoconference intervention (VCI) to reduce perinatal depression symptoms (PDS) and anxiety (a highly co-morbid condition) by conducting a randomized controlled trial among women experiencing mild to moderate PDS, as measured by the Edinburgh Postnatal Depression Scale (EPDS). Furthermore, we propose to evaluate differences in response to the VCI between subgroups of childbearing women; Hispanic and North European Descent populations, and rural and urban-dwelling.

Specific aims of the study include:

Aim 1: Evaluate the effectiveness of a VCI to reduce PDS and anxiety, as measured by EPDS and Generalized Anxiety Disorder-7 Item (GAD-7) scores across pregnancy and the postpartum. Methods: Pregnant women of all gestational age up to 6 months postpartum (n = 240) who screen positive for mild to moderate PDS (EPDS scores 9–20) will be randomly assigned to VCI or AC for eight weeks. Both groups will continue with standard care as directed by their primary/prenatal care providers. The EPDS and GAD-7 will be administered at three time points during pregnancy and at 2, 4, and 6 months postpartum. Hypothesis: Women participating in the VCI will have significantly lower post intervention EPDS and GAD-7 scores across pregnancy and postpartum than women in the AC group.

Secondary Aim 1: Explore differences in the effectiveness of the VCI to reduce PDS and anxiety across women who enroll at different stages of their pregnancy or postpartum periods.

Aim 2: Evaluate the interaction of the VCI with specific subgroups: ethnicity (Hispanic, North European descent), geographic location (rural, urban), and the outcome of PDS as measured by EPDS and GAD-7 scores across pregnancy and postpartum. We will oversample in Hispanic and rural populations to ensure sufficient representation from diverse groups. Hypothesis: Women will demonstrate differences in EPDS and GAD-7 scores across pregnancy and postpartum, dependent on their study group membership.

Secondary Aim 2: Explore an additional subgroup analysis, namely between those who are and who are not taking medication at the time of screening.

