#### Group VCI Sessions

Using the UTN-supported Acano platform, women will attend weekly, 1-hour videoconference sessions with 4–5 other participants (maximum  $n = 6$ ), for a total of 10 sessions: one initial session for getting acquainted with one another and the program, eight sessions for engagement in the VCI intervention, and a follow-up “reunion” 6–8 weeks after the last session. Members of the Latina community will be enrolled in study groups that will include 15 minutes of extra mental health content, based on recommendations from the focus groups done in the community and their needs (actual intervention content will not be altered, just additional mental health background will be included). Participants will attend each session using their own Internet connection and electronic device (computer, laptop, electronic tablet, smart phone) to connect to Acano. Alternatively, participants can connect via the Internet without video, or as a last resort can simply call in by telephone landline or basic mobile phone. The intervention is a standardized and manualized program called UPLIFT (Using Practice and Learning to Increase Favorable Thoughts), developed and evaluated by [name]. UPLIFT is an 8-week group intervention based on CBT and MBP, therapies with demonstrated effectiveness in the prevention and treatment of depression. Originally developed as an online and telephone-based approach, we have adapted and piloted the program for videoconference use in a pregnant population. Our revised telehealth approach has several advantages over conventional in-person therapies, including (1) improved accessibility to therapy among working, low-income, and rural-dwelling mothers, and those with time, childcare, and transportation barriers; (2) the ability to develop a supportive community among other mothers of similar risk status and life circumstances; (3) the ability for women to build an effective skill set for the prevention and treatment of depression that can last a lifetime; (4) the addition of nonverbal communication between group participants and the facilitator when videoconferencing is used; and (5) sufficient time to acquire and practice Mindfulness-Based Cognitive Behavioral Therapy skills early in pregnancy, prior to baby's arrival and the postpartum period, when the risk of depression is highest. After the 8-week intervention, a cohort “reunion” will be held approximately 6–8 weeks after the last session. The approach just described was developed based on the strong recommendations of participants in our pilot studies, including the initial pre-UPLIFT meeting

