#### Participant-Completed Questionnaires

Questionnaires will be completed by participants via a secure, Web-based data management system (REDCap). Women in all study groups will receive an emailed link to the questionnaire. Study questionnaires are to be completed at six time points: T1 = enrollment; T2 = after group session 9; T3 = 2 months post session 9 T4 = 4 months post session 9; T5=6 months post session 9; T6= 8 months post session 9. In addition to participant demographics, questionnaires will include the EPDS as a measure of the primary outcome of interest: depressive symptoms, as well as the GAD-7 as a measure of comorbid anxiety (GAD-7 is a validated survey). To document the standard of care that all participants receive during study participation, the questionnaire at all six-time points also asks participants to report whether they (1) received a diagnosis of depression, anxiety, or other mental health condition; (2) were prescribed or initiated any medication for depression or anxiety; (3) were referred to and/or engaged in mental health services; and/or (4) have engaged in any type of nonpharmacological therapies for depression/anxiety during the study. If a participant does not have an email address, study staff will assist her to establish and access a free email address. All participants will receive instruction on how to access and complete the study questionnaires. The entire questionnaire takes approximately 15 minutes to complete. Participants receive \$20 for each questionnaire completed.

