## **Data Analysis**

We will use multilevel generalized mixed modeling under an intent-to-treat approach to compare the outcome measures of EPDS and GAD-7 between group 1 (VCI) and Group 2 (AC) at six-time points during pregnancy and postpartum. This is an appropriate statistical approach for the described RCT protocol. Sensitivity analysis was conducted with G-Power 3.1. We used RMANOVA with 6 total measures as a conservative power analysis for our mixed-effects model. The sample is powered for the fixed effect of Intervention X Time. For study aim 1: Using RMANOVA with alpha = 0.5, 6 total measures, 0.3 for correlation between repeated measures, and a sample size of 192 total participants gives greater than 90 percent power to detect an effect size of 0.1, which is a net decrease in EPDS and GAD-7 of roughly 1 point decrease per time point, assuming a standard deviation of 5. For study aim 2: For the stratified samples of urban/rural or Hispanic/NED, we have greater than 80 percent power to detect the same Intervention X Time effect size of 0.1.

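### Both arms are delivered in groups, but the plan decides whether to model the groups after seeing an imprecise ICC, and its Aim 1 power figure has no clustering term

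*Combined protocol and SAP*

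**What the plan says.** Delivery is by group in both arms. Under Group VCI Sessions, "women will attend weekly, 1-hour videoconference sessions with 4–5 other participants", with a maximum of six per group. The Attention Control section also describes delivery by group videoconference but states no group size.

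The Data Analysis text under Statistical Methods, Data Analysis and Interpretation specifies a multilevel mixed model under intent-to-treat. On groups it gives this purpose: "To assess whether we will need to nest participants within clusters (Level 3, group-level) given that the intervention/control are administered in groups". The step that follows is a further fit of the model with a level for group, from which the ICC is obtained. It gives no threshold, test or default for what happens next.

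The power paragraph is in the Data Analysis section under Procedures. It says "The sample is powered for the fixed effect of Intervention X Time" and that "a sample size of 192 total participants gives greater than 90 percent power to detect an effect size of 0.1". Its inputs are alpha (printed as 0.5), six measures, a correlation of 0.3 and a standard deviation of 5. It gives no ICC and no group size. The enrolment goals are "for a total of 240 participants", and nothing explains the gap between 192 and 240.

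The Aim 1 hypothesis reads "Women participating in the VCI will have significantly lower post intervention EPDS and GAD-7 scores across pregnancy and postpartum". Under Participant-Completed Questionnaires the visits begin "T1 = enrollment; T2 = after group session 9", so T1 comes before any group has met.

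**The concern.** Women who share a group and a facilitator may have correlated outcomes. If that correlation is real and the model leaves it out, standard errors for a between-arm comparison are too small. The plan recognises this and will look at the ICC. But with about 20 small groups per arm the ICC is poorly estimated, so a low or non-significant value is weak evidence that groups can be left out. Some retention rules hold the 5% level and others do not, and the plan names none.

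The second issue is power. Group delivery reduces the information per woman, and the Aim 1 calculation makes no allowance for it.

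**Working it through.** **1. Reproduce the stated power.** Inputs from the power paragraph: f = 0.1, N = 192, six measures, correlation 0.3. I take alpha as .05, since 0.5 is printed. For the within-between interaction:

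lambda = f² x N x 6 / (1 - 0.3) = 0.01 x 192 x 6 / 0.7 = 16.46, with df 5 and 5 x 190 = 950.

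Power from the noncentral F is 89.8%, and 194 women are needed to reach 90%. At the printed alpha of 0.5 it is 99.6%. The stated figure is therefore the unclustered one.

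**2. Add clustering to the power.** The ICCs are assumed. Divide lambda by the design effect 1 + (m - 1) x ICC. For 192 women in 40 groups, m = 192/40 = 4.8. For 240 in 40 groups, m = 6. The control arm's groups are taken to match the VCI arm's.

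| ICC | Design effect, m = 4.8 | Power, N = 192 | Design effect, m = 6 | Power, N = 240 |
|---|---|---|---|---|
| 0 | 1 | 89.8% | 1 | 95.7% |
| .02 | 1.076 | 87% | 1.10 | 94% |
| .05 | 1.19 | 83% | 1.25 | 90% |
| .10 | 1.38 | 76% | 1.50 | 83% |

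At ICC .05, 240/1.25 = 192, so full analysis of 240 returns almost exactly the unclustered figure at 192.

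The simple design effect is an approximation for an interaction. If the group effect starts at T2 and persists, power at N = 192 is 88.5/86.8/84.4% when the treatment effect grows linearly and 86.7/81.8/73.8% when it is a step at T2.

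**3. Precision of the ICC.** With 20 groups of 5 per arm and a true ICC of .05, 95% of estimates from one value per woman lie between -.06 and .17. Using each woman's T2-T6 mean narrows this to about -.01 to .11.

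**4. Type I error, T2-T6 mean.** This comparison is inferred from the Aim 1 hypothesis; neither Data Analysis section names it. Assumptions: 20 groups of 5 per arm, correlation .3 between visits, group effect present from T2.

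The bound with groups ignored can be checked by hand. With unit individual variance, the variance of a five-visit mean is (1 + 4 x 0.3)/5 = 0.44. At ICC .05 the group variance is .05/.95 = .0526. The ICC of the mean is .0526/(.44 + .0526) = .107, and the design effect is 1 + 4 x .107 = 1.43. A nominal 5% test then rejects when |z| exceeds 1.96/√1.43 = 1.64, which is 10%.

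The simulated rates, with a group-level t-test standing in for the three-level model, are:

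| Rule (all assumed) | ICC .02 | .05 | .10 |
|---|---|---|---|
| Always keep | 5.1% | 4.9% | 4.8% |
| Keep if variance estimate is positive | 4.9% | 4.9% | 4.8% |
| Keep if p < .05, ICC from T1-T6 | 6.4% | 7.0% | 6.0% |
| Keep if p < .05, ICC from T2-T6 | 6.3% | 6.1% | 5.5% |
| Ignore groups (bound) | 7.1% | 10.0% | 14.4% |

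The p < .05 rule drops the level in 84/57/17% of trials when T1 is included and in about 79/41/6% when it is not.

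**5. Type I error, Intervention x Time, groups ignored.** It is about 5% if the group effect is constant over T1-T6, because the effect cancels. It is 5.2/6.2/7.5% if the effect starts at T2 and persists, and 6.4/8.7/12.7% if half persists and half varies by visit. In the extreme case of effects unrelated between visits it is 7.3/11.3/18.4%. The retention rules in step 4 were not compared for this term.

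**The case against.** The strongest reply is that the plan already deals with clustering. It recognises group delivery in both arms and commits to fitting the extra level and calculating the ICC. That is right, and it limits the point. A reader might infer that the trial will ignore groups and run at 7 to 15% type I error. The documents do not support that: they never say groups will be left out, so those rates are a bound.

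A sensible unwritten rule might also do no harm. Keeping the level whenever its variance estimate is positive held about 5%. This stands too. What remains is that nothing commits the team to that rule rather than to a significance test.

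A reader might further infer that the powered Intervention x Time test is distorted by the retention decision. That has not been shown. The rule comparison is for a T2-T6 mean, and even ignoring groups altogether does little to the interaction unless group effects vary from visit to visit.

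Finally, a reader might conclude that the trial is underpowered or must enrol more women. That does not follow. The 240 may absorb the loss up to an ICC of about .05. Whether it does depends on how many are analysed, which the documents leave open.

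**Conclusion.** The point holds as a correctable weakness of modest size. The primary model depends on a look at the data with no written rule. Under one common rule, the cost for a post-intervention mean comparison is about 5.5 to 7% type I error in place of about 5%. The Aim 1 power at 192 takes no account of groups. A fair statement would be about 87/83/76% for 192 analysed and 94/90/83% for 240, at ICC .02/.05/.10.

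The omissions are certain from the text; the size of their effect is not. It rests on assumed ICCs, an assumed control-arm group size equal to the VCI arm's, alpha of .05, and an inferred comparison. The simulations also leave out the overlap between group and ethnicity that arises because Latina women join groups with extra content.

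**What to change.** In Data Analysis under Statistical Methods, replace the sentence that begins "To assess whether we will need to nest participants within clusters (Level 3, group-level) given that the intervention/control are administered in groups" with: *The group-level random effect is kept in the primary model in both arms whatever the estimated ICC, with small-sample (Satterthwaite or Kenward-Roger) degrees of freedom, and the ICC is reported.* If the team prefers a data-based decision, the rule should be written down before the data are seen.

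In the power paragraph, restate Aim 1 power over an assumed ICC range, such as .02 to .10, with a stated group size for each arm. Say whether 192 or 240 is the number expected in the analysis.

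The cost is small. The three-level model is already planned and no added enrolment is needed. Group membership must be recorded in both arms, intervals will be slightly wider, and the stated power will look less favourable. The group variance will sometimes be estimated at zero: in about 23/5/0.2% of simulated trials at ICC .02/.05/.10, using T2-T6 means.
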